Participant visits will occur at Months 72, 84, 96 and 108 (+/- 1 month) following the date of the surgical procedure for NTMT-01.

Cohort 2 - Prospective, multi-center, single-masked sham-controlled study. All participants will have been enrolled (undergone a NT-501 implant and/or sham procedure) in the *A Phase 2 Multicenter Randomized Clinical Trial of Ciliary Neurotrophic Factor (CNTF) for Macular Telangiectasia Type 2 (MacTel NTMT-02)* protocol and have agreed to continue in this follow-up study.

In the event that the NTMT-02 study is positive, Cohort 2 participants who received sham only may be eligible for active treatment in the control/non-treated eye.

Participant visits will occur at Months 36, 48, 60 and 72 (+/- 1 month) following the date of the surgical procedure for NTMT-02.

Sample Size:

Cohort 1 - 7 participants (7 study eyes) – previously enrolled in NTMT-01 protocol

Cohort 2 – 66 participants (98 study eyes) – previously enrolled in NTMT-02 protocol

Diagnosis and Key Eligibility Criteria: Previously enrolled in NTMT-01 or NTMT-02 protocols

Investigational Product: NT-501 implant

Duration of Treatment:

Cohort 1 - Visits to continue until Month 108 from date of study procedure, with annual analyses at Months 72, 84, 96, and 108.

Cohort 2 - Visits to continue until Month 72 from date of study procedure, with annual analyses at Months 36, 48, 60, and 72.

Number of Centers: 8 sites in the United States and 3 sites in Australia

Study Outcomes:

Cohort 1: The following efficacy outcomes as outlined in the NTMT-01 Protocol will continue to be analyzed to investigate the efficacy of Ciliary Neurotrophic Factor (CNTF) produced by NT-501 (all changes relative to NTMT-01 baseline measurements):

- Change in the ellipsoid zone (area of IS/OS loss) from baseline to Months 72, 84, 96 and 108.
- Change in retinal sensitivity (dB) as measured by microperimetry from baseline to Months 72, 84, 96 and 108.
- Proportion of study eyes with a 35% or more increase from baseline in the ellipsoid zone (area of IS/OS loss) at Months 72, 84, 96 and 108.
- Change in best corrected visual acuity (BCVA) from baseline to Months 72, 84, 96 and 108.
- Proportion of study eyes with 15 or more letter loss from baseline in BCVA at Months 72, 84, 96 and 108.
- Proportion of study eyes with 10 or more letter loss from baseline in BCVA at Months 72, 84, 96 and 108.

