3.1 Encapsulated Cell Technology (ECT)

This study is designed to provide long term observation of the ongoing effect of CNTF as delivered continuously via the NT-501 implant in patients with MacTel type 2. MacTel type 2 is a slowly progressive condition which may take many years to develop clinical symptoms and signs.

The Phase II NTMT-02 trial was limited to 24 months of controlled observation. While it is anticipated that two years of controlled observation should be sufficient to determine efficacy, it is possible that a longer period is necessary to observe a meaningful separation between the groups. This extension study provides the opportunity for that continued observation.

Previous experience with the NT-501 implant in studies of participants with geographic atrophy or retinitis pigmentosa suggests that the implant is capable of delivering detectable CNTF for up to 66 months. Output of CNTF from explanted devices, along with vitreous levels of CNTF, is consistent with the histologic findings at these various time points; the cells remain healthy and productive within the membranes (capsules), and continue to produce and deliver CNTF. These data support the hypothesis that NT-501 will continue to provide similar levels of CNTF to the

study eyes during this prolonged follow up period. Mean duration of implantations together with explant and vitreous CNTF levels are shown in Table 2.

Table 2: Ex vivo production rates and vitreous CNTF concentrations at the time of NT-501 explantation

Implant Duration	Explant (ng/ day)	#	Vitreous (pg/mL)	#
6 months	1.54 ± 0.54	(5)	58 ± 0	(1)
12-13 months	2.09 ± 0.59	(11)	64 ± 0	(2)
18-20 months	1.78 ± 0.86	(7)	57 ± 0	(1)
24 months	1.08 ± 0.48	(11)	46 ± 0	(1)
30-33 months	1.10 ± 0.73	(6)	17 ± 0	(1)
45 months	1.25 ± 0.00	(1)	55 ± 0	(1)
54 months	0.70 ± 0.04	(2)	---	
66 months	1.16 ± 0.00	(1)	36 ± 0	(1)

The Phase I NTMT-01 trial designed to assess the safety and tolerability of the NT-501 implant in patients diagnosed with MacTel type 2 has completed enrollment (N=7) and follow-up continues. No serious adverse reactions have been reported to date. Preliminary data confirm that the progression of visual impairment is slow in MacTel type 2. This is consistent with the findings of Heeren et al (2015) who suggested that patients with MacTel type 2 require prolonged follow up for appropriate evaluation of functional loss.

4 Study Objectives

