6.8 Exam Requirements

The following are examinations to be performed at the times indicated in Appendix 1.

1. Informed Consent and Eligibility Criteria Review
2. Demographics and Participant Contact Information Review
3. Medical/Ophthalmic History Review (carried over from NTMT-01 or NTMT-02)
 - Adverse events noted during the NTMT-02 and NTMT-01 study period and up to the first Extension Study visit will be added as Medical/Ophthalmic History as applicable.
4. Adverse Event Assessment (from the date of the NTMT-01/02 Extension Study consent)
5. Concomitant Medications
6. Complete Ophthalmic Examination including:
 - Manifest refraction
 - BCVA (This test will be performed by a masked certified technician)
 - Goldmann applanation tonometry
 - Slit lamp biomicroscopy
 - Dilated fundus examination
 - Implant site clinical examination
7. Ophthalmic Assessments including:
 - Microperimetry
 - Spectral Domain Optical Coherence Tomography (SD-OCT)
 - Fundus Autofluorescence imaging
 - Digital Color Fundus photographs

- Adaptive Optics Scanning Laser Ophthalmoscopy (AOSLO), in selected participants
 - Participants who underwent AOSLO for NTMT-02 will undergo a separate consent process at the AOSLO Center if they agree to continue participating.

8. Reading Speed –NTMT-02 (Cohort 2) participants only

- Monocular and binocular reading speed will be assessed using IReST cards. Reading speed will be used to document the participant's functional status with an important everyday visual task.

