8.1 Efficacy Outcomes

Cohort 1

Efficacy outcomes to investigate the efficacy of CNTF produced by NT-501 include (all changes relative to NTMT-01 baseline measurements):

- Change in the ellipsoid zone (area of IS/OS loss) from baseline to Months 72, 84, 96 and 108.
- Change in retinal sensitivity (dB) as measured by microperimetry from baseline to Months 72, 84, 96 and 108.
- Proportion of study eyes with a 35% or more increase from baseline in the ellipsoid zone (area of IS/OS loss) at Months 72, 84, 96 and 108.
- Change in BCVA from baseline to 72, 84, 96 and 108.

- Proportion of study eyes with 15 or more letter loss from baseline in BCVA at 72, 84, 96 and 108.
- Proportion of study eyes with 10 or more letter loss from baseline in BCVA at 72, 84, 96 and 108.

Cohort 2

The outcomes to investigate long term efficacy of CNTF or NT-501 include (all change relative to NTMT-02 baseline measurements):

- Change in ellipsoid zone (area of IS/OS loss) from baseline to Months 36, 48, 60 and 72.
- Change in retinal sensitivity (dB) as measured by microperimetry from baseline to Months 36, 48, 60 and 72.
- Proportion of study eyes with a 35% or more increase from baseline in the ellipsoid zone (area of IS/OS loss) at Months 36, 48, 60 and 72.
- Change in BCVA from baseline to Months 36, 48, 60 and 72.
- Proportion of study eyes with 15 or more letter loss from baseline in BCVA at Months 36, 48, 60 and 72.
- Proportion of study eyes with 10 or more letter loss from baseline in BCVA at Months 36, 48, 60 and 72.
- Change in reading speed from baseline to Months 36, 48, 60 and 72.

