8.2 Analyses in Support of the Efficacy Outcomes

Cohort 1

For continuous measures mean, median and distribution of change from baseline in BCVA, and enlargement of inner/outer segment discontinuity as measured by SD-OCT will be computed separately for study eyes and fellow eyes. For dichotomous outcomes proportions along with 95% confidence intervals will be computed separately for study eyes and fellow eyes.

Cohort 2

Continuous efficacy measures will be assessed using mixed effects models with an overall Type I error rate of 0.05 (no adjustments of the type I error rate will be made). Due to clustered data (data from two eyes for a percentage of the participants), the variability associated with the estimates of effect (mean difference) from a fixed effects model is likely to be biased, leading to

incorrect test statistics and confidence intervals. For example, if the correlation from paired eyes is ignored, the standard error for the treatment effect is likely to be overestimated when paired eyes from the same participant are in different treatment groups. For this reason, the unpaired t-test for the comparison of means between two treatment groups is not appropriate as it assumes that observations from the same cluster are independent. The appropriate statistical analysis of clustered data should take such correlation into consideration which can be accomplished for continuous outcome measures using a mixed effects model. The mixed effects model will incorporate both random (accounting for the correlation between eyes) and fixed effects (treatment) into the model and will be estimated with accompanying 95% confidence intervals and compared between treatment groups. For dichotomous outcomes, logistic regression incorporating the generalized estimation equation (GEE) methodology with accompanying 95% confidence intervals will be performed to determine if there are significant differences in the odds between the two treatment groups.

The efficacy analyses will be repeated to investigate the strength of potential predictors using multivariable mixed effects models or multiple logistic regression models. Examples of potential predictors include the following: baseline visual acuity, clinical site, participant's age at enrollment and gender.

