8.3 Sample Size

A sample size of 66 participants, the number of participants enrolled in the NTMT-02 study and 7, the number of participants enrolled in the NTMT-01 study, will be eligible for enrollment.

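### The main Cohort 2 mixed model for continuous outcomes omits each outcome's own baseline value, giving up possible precision in a sample that cannot grow

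*Combined protocol and SAP*

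**What the plan says.** Section 8.2 (Cohort 2) sets out the main model for continuous measures: "The mixed effects model will incorporate both random (accounting for the correlation between eyes) and fixed effects (treatment) into the model". No fixed effect other than treatment is named. Treatment differences are to be reported with 95% confidence intervals.

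Section 8.1 defines the Cohort 2 outcomes as changes: "all change relative to NTMT-02 baseline measurements". The continuous ones are ellipsoid zone area, retinal sensitivity, BCVA and reading speed.

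Covariates come in only at a later step of Section 8.2: "The efficacy analyses will be repeated to investigate the strength of potential predictors". The list given there is illustrative: "Examples of potential predictors include the following: baseline visual acuity, clinical site", followed by age and gender. Baseline visual acuity is the own baseline for BCVA alone. Baseline ellipsoid zone area, retinal sensitivity and reading speed are not named as covariates anywhere.

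Section 8.3 fixes the pool: "A sample size of 66 participants, the number of participants enrolled in the NTMT-02 study". The Study Summary gives 98 study eyes for these 66 participants.

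**The concern.** Subtracting baseline and adjusting for it are different operations. A change score fixes the coefficient of baseline at 1. A model that includes baseline estimates that coefficient and removes whatever part of the change is still related to the starting value. If change is correlated with baseline, for instance because larger lesions grow faster or because of regression to the mean, the unadjusted model leaves that variation in the residual and the interval is wider than it need be. Any chance imbalance in baseline between arms also stays unadjusted.

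This matters more here than in a trial still being sized. Cohort 2 is closed, and withdrawal over a further 48 months can only shrink it, so analysis is one of the few remaining sources of precision. The repeat analyses do not settle the matter: their stated purpose is to study predictors, their covariates are examples, and nothing says which estimate leads if the unadjusted and adjusted results differ.

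**Working it through.** The documents state no power, effect size, SD or correlation, so there is no planned figure to reproduce. The question is how much the interval changes when baseline is added.

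**Inputs from the documents.** 66 participants and 98 study eyes. 98 − 66 = 32 participants with two study eyes; 66 − 32 = 34 with one.

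**Assumptions.** One eye per arm in two-eye participants, 1:1 allocation in one-eye participants, complete data at the visit, normal errors. Two unknowns are varied: r, the correlation between baseline and change, and the between-eye correlations.

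**Approximate formula.** Variance ratio, adjusted to unadjusted, ≈ 1 − r². At r = 0.2, 0.3 and 0.5 this gives 0.96, 0.91 and 0.75, before the cost of the extra parameter.

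**Simulation of this design.** Per-visit REML model with compound symmetry between eyes and a Satterthwaite t reference, 4,000 replicates per setting. Between-eye correlation is 0.5 for both baseline and residual:

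| r | Variance ratio | CI-width ratio | 66 ÷ variance ratio |
|---|---|---|---|
| 0 | 1.010 | 1.005 | – |
| 0.1 | 1.001 | 1.001 | – |
| 0.2 | 0.972 | 0.986 | 67.9 |
| 0.3 | 0.919 | 0.959 | 71.8 |
| 0.4 | 0.850 | 0.922 | 77.6 |
| 0.5 | 0.757 | 0.870 | 87.2 |

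The last column is the unadjusted sample with the same information: about 2, 6, 12 and 21 more participants than 66 at r = 0.2 to 0.5.

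Over four sets of between-eye correlations (baseline, residual: 0.5, 0.5; 0.7, 0.5; 0.5, 0.7; 0.3, 0.3), the interval narrows by 1–2.5% at r = 0.2, 3–6% at 0.3 and 9–18% at 0.5. At r = 0 it is 0.4–0.7% wider. Type I error averages 0.052 for both models.

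**What r might be.** Let c be the baseline-to-follow-up correlation and s the ratio of follow-up SD to baseline SD. Then r = (cs − 1) / √(s² + 1 − 2cs).

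- s = 1, c = 0.95, 0.9, 0.8, 0.7, 0.5: |r| = 0.16, 0.22, 0.32, 0.39, 0.50.
- s = 1.5, c = 0.8, 0.9: r = 0.22, 0.47.
- s = 1.25, c = 0.8: cs = 1, so r = 0 and nothing is gained.

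Section 3.1 says: "Preliminary data confirm that the progression of visual impairment is slow in MacTel type 2". If that means c = 0.9 with s = 1 (assumed), |r| = 0.1/√0.2 = 0.22 and the interval narrows by about 2%.

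**Cross-check.** With s = 1 the formula reduces to a variance ratio of (1 + c)/2. A separate maximum-likelihood simulation of the same design, with between-eye correlations of 0.3 and 0.6, gave 0.76 and 0.77 at c = 0.5 (formula 0.75), 0.84 and 0.83 at 0.7 (0.85), and 0.96 and 0.94 at 0.9 (0.95). The random effect for eyes does not absorb the gain.

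**The case against.** The planned analysis contains no error: it is unbiased, its type I error matches that of the adjusted model, and no stated precision target is missed. The gain may be negligible. On the one relevant fact in the documents, slow progression, it is about 2%, and ordinary inputs (c = 0.8, s = 1.25) give none. The larger figures need r near 0.5, which with equal SDs means a baseline-to-follow-up correlation of only 0.5. The naming of treatment may be shorthand, and for BCVA an own-baseline model is already foreseen among the repeat analyses. If the NTMT-02 analysis was unadjusted, a new main model would break continuity, and Month 24 results may be known by the time it is chosen.

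Much of this stands. It makes the point one of efficiency and the equivalent-participant figures illustrative, and the simulation's complete-data and 1:1 assumptions are idealised. It does not remove the point. If the wording is shorthand, one sentence settles it. The repeat analyses are for studying predictors, and for three of the four continuous outcomes they do not name the relevant baseline. Continuity is kept by reporting the unadjusted estimate too. The possible loss is under 1% of interval width, against a possible gain several times larger. Knowledge of the Month 24 results is a reason to fix the choice before any extension analysis.

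**Conclusion.** The concern holds. The main Cohort 2 model for continuous outcomes omits the outcome's own baseline, the data are already collected, and the sample cannot grow. The consequence is a possible loss of precision, not bias. Its size cannot be taken from the documents. Under the stated design assumptions it ranges from nothing (r near 0) through 3–6% of interval width at r = 0.3 to 9–18% at r = 0.5, with about 2% if slow progression means a baseline-to-follow-up correlation of 0.9 and equal SDs. The change should be made because it is cheap and its downside is very small; a large gain cannot be promised.

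**What to change.** In Section 8.2, state that the main mixed model for each continuous Cohort 2 outcome (ellipsoid zone area, retinal sensitivity, BCVA, reading speed) includes the NTMT-02 baseline value of that same outcome as a fixed covariate. Name this as the main estimate before the Month 36 analysis and report the unadjusted estimate beside it. Keep the other covariates for the repeat analyses.

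For reading speed, match the baseline to the measure analysed, since Section 6.8 says: "Monocular and binocular reading speed will be assessed using IReST cards". Whether a binocular value can carry a treatment contrast in participants with one eye per arm is a separate question, which the covariate does not resolve.

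Leave the GEE logistic models as planned. A baseline-adjusted version could be a sensitivity analysis only, noting that its odds ratio becomes conditional and may be unstable with few events.

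Optionally, and descriptively, report the treatment difference in change from Month 24 to Months 36–72, because a cumulative Month 72 difference cannot by itself show benefit gained after Month 24. Possible active treatment of sham-only participants (Section 5) and unmasking (Section 6.7) limit its interpretation.

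The core change costs a few words of the plan and one parameter per model. No eye is lost, because an eye with a change score already has a baseline. If baseline is unrelated to change, the interval widens by less than 1%.

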8.3 Sample Size

A sample size of 66 participants, the number of participants enrolled in the NTMT-02 study and 7, the number of participants enrolled in the NTMT-01 study, will be eligible for enrollment.

8.4 Safety Analysis

Long term safety will be assessed through the summary of ocular and non-ocular adverse events, serious adverse events and pre-specified safety outcome as defined in Section 6.1.3 and will include frequency and descriptive tabulation. No formal statistical analysis will be employed. Safety analyses will include all participants who received the implant or sham.

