6.1.3 Safety Outcomes

The following ocular events (regardless of attribution) will be considered safety outcomes for both Cohorts if they occur:

- Rejection or extrusion of the NT-501 device.
- Development of peri-implant fibrosis, which either blocks the visual axis of the implanted eye or affects the lens or retina (minor/moderate fibrosis around the implant and/or the attachment point is an expected possibility and will be considered safe on ocular function). Attention should focus on fibrosis that may detach the retina.
- Development of choroidal or retinal neovascularization in the study eye.
- Adverse events affecting ocular function, which are different from those expected in the normal course of MacTel, which are potentially related to the surgical procedure, implant or CNTF including:
 - Endophthalmitis
 - Vitreal inflammation
 - Tractional retinal detachment

- Sectorial lens opacification
- Intraocular hemorrhage
- High or low Intraocular pressures
- Dry eye
- Self-reported change in dark adaptation
- Miosis
- Persistent chemosis
- Scleral leak

All adverse events (AEs) will be captured from the date of the Extension Study Consent whether or not considered to be related to the surgical procedure, NT-501 device, or CNTF. All adverse events occurring between the final NTMT-01 or NTMT-02 study visit will be considered part of the participants' Medical and/or Ophthalmic History.

An attempt will be made to differentiate between treatment-related AEs and AEs considered to be part of the normal progression of the disease. In addition, for treatment-related AEs, an attempt will be made to differentiate those the Investigator believes are due to the procedure, NT-501 device, or CNTF.

Analysis of safety events will be conducted separately for each Cohort.

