6.4 Study Procedures

All study procedures will be carried out for both eyes at each visit. This will include both the study eye(s) and the fellow eye as applicable.

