6.7 Masking

For participants in Cohort 2 there are different levels of masking within the study. The site staff refractionist, visual acuity examiner and photographers/imagers must remain masked to treatment assignment (NT-501 implant or sham procedure) for all visits. The Ophthalmologist, Surgeon and Clinic Coordinator will be unmasked to treatment assignment.

To ensure that the refractionist, visual acuity examiner and photographers/imagers remain masked to the randomized assignment, the Ophthalmologist, Surgeon and Clinic Coordinator are not to discuss the treatment received with the refractionist, visual acuity examiner and photographers/imagers.

All personnel in the Central Image Reading Center will be masked to whether the participant received the NT-501 implant or sham in a study eye(s).

Masking will remain as described above until all 66 participants in the NTMT-02 protocol have completed their original NTMT-02 Protocol Month 24 visit and data analysis has been completed. At that time, the Principal Investigators will be informed by the Sponsor that they

may unmask the participants. They may choose to do this at the participants' next scheduled visit or in a personalized communication to the participant. The sites will notify the Coordinating Center of the unmasking as outlined in the Manual of Procedures.

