Guidelines for Determining when Changes in Pre-Existing Conditions are Considered Adverse Events

Adverse events include illnesses with onset during the study or exacerbations of pre-existing illnesses. Exacerbation of pre-existing illness is defined as a clinically relevant increase in the severity of the illness as compared to the start of the study and should be considered when a participant requires new or additional treatment for that illness. Investigators should use the following guidelines to assess when an adverse event needs to be reported for a condition which results in a change to an ongoing medication and/or addition of a new medication:

- Addition of a new medication and/or change in ongoing medication due to an untoward (unfavorable and unintended) change in a participant's medical health for a disease/condition documented as ongoing at baseline.
- Addition of a new medication due to an untoward (unfavorable and unintended) change in a participant's medical health for a disease/condition not present at baseline.

Guidelines for Assessing Intensity of an Adverse Event

The Investigator should use the following definitions when assessing Intensity of an Adverse Event:

- **MILD:** Transient (< 48 hours) or mild discomforts, no or minimal medical therapy or intervention required, hospitalization not necessary, no or little limitation in normal activities.

- MODERATE: Mild to moderate limitation in activity, some assistance may be needed; possibly none but usually minimal intervention/therapy required; hospitalization possible.
- SEVERE: Marked limitation in activity, some assistance usually required; medical intervention/therapy required; hospitalization possible or likely.
- LIFE THREATENING: Extreme limitation in activity, significant and immediate assistance required; significant medical/therapy intervention required to prevent loss of life; hospitalization, emergency treatment or hospice care probable.
- FATAL: Death

Guidelines for Determining Causality of an Adverse Event

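### The Cohort 2 safety tables name no NT-501 versus sham split for ocular events, and the intraocular pressure readings taken at every visit have no planned summary

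*Combined protocol and SAP*

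**What the plan says.** **Planned tables.** Section 8.4 rests long-term safety on "adverse events, serious adverse events and pre-specified safety outcome as defined in Section 6.1.3 and will include frequency and descriptive tabulation". It plans no formal analysis and includes everyone who received implant or sham. Section 8.5 splits ocular events by cohort, by study eye(s) versus fellow eye and by severity, and adds a summary of events reported as related to the implant or its surgery. Neither section mentions a split by treatment received.

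**Who is masked.** Section 6.7 describes Cohort 2 study eyes as having received either the implant or sham. It also states: "The Ophthalmologist, Surgeon and Clinic Coordinator will be unmasked to treatment assignment".

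**Pressure.** Goldmann tonometry is scheduled at Visits 1 to 4 (Section 6.9, Appendix 1), and Section 6.4 says: "All study procedures will be carried out for both eyes at each visit". Section 6.1.3 lists "High or low Intraocular pressures" among examples of adverse events affecting ocular function, with no numerical limit. Under Section 7.3, a changed ophthalmological assessment counts as an adverse event when the investigator judges it clinically significant and it needs intervention. No section plans a summary of the measured values. Section 8.2 does spell out such a summary for an efficacy measure in Cohort 1: "For continuous measures mean, median and distribution of change from baseline in BCVA".

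**The concern.** Long-term safety is part of the first objective, and Cohort 2 is described as sham-controlled. The reason to keep sham eyes under the same examinations is to learn whether what happens in implanted eyes also happens without the implant. A table that separates only study from fellow eyes cannot answer that, because both treatments are on the study-eye side.

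The related-event summary is a partial substitute at best. It depends on an investigator's opinion about cause. If the investigator is one of the ophthalmologists or surgeons covered by Section 6.7, that person knows which eye holds the implant.

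For IOP there is a second gap. The reading is taken on a fixed schedule in every eye, yet it reaches the safety tables only after someone decides that it is an event. Two investigators can decide differently about the same reading. A modest shift that nobody reports would not appear in the tables, although the numbers to show it are in the database.

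**Working it through.** The plan gives no safety rate or IOP figure to reproduce. The check has three parts.

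**1. Eye counts** (Study Summary: Cohort 1 has 7 participants and 7 study eyes; Cohort 2 has 66 participants and 98 study eyes)

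- Cohort 2 participants with two study eyes: 98 − 66 = 32, which is 32/66 = 48%. They have no non-study eye.
- Cohort 2 participants with one study eye: 66 − 32 = 34, giving 34 non-study fellow eyes (132 − 98).
- IOP readings if everyone enrols and attends all four visits: study eyes (98 + 7) × 4 = 420; non-study eyes (34 + 7) × 4 = 164; total 584.

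**2. What each planned split can show in Cohort 2**

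| Split in Section 8.5 | Separates NT-501 from sham? |
|---|---|
| Study eye(s) versus fellow eye | No: sham eyes are study eyes, and 32 participants have no fellow eye |
| Severity | No |
| Related to implant or surgery | Only through the investigator's attribution |

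**3. Illustrations (assumptions, not findings)**

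The documents do not give the number of eyes per arm. Assume that each of the 32 two-eye participants has one eye in each arm; Section 8.2 mentions such pairs as an example. Let the 34 single eyes divide in any way. NT-501 eyes then number from 32 + 0 = 32 to 32 + 34 = 66. The extremes are unlikely in a randomised trial; 49 and 49 is the middle.

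- If events occurred only in NT-501 eyes, the combined row would show n/98 of the NT-501 rate: 32/98 = 33%, 49/98 = 50%, 66/98 = 67%.
- Six NT-501 eyes with an event and no sham eyes: the NT-501 rate is 6/66 = 9.1%, 6/49 = 12.2% or 6/32 = 18.8%, against 0% in sham. The combined row reads 6/98 = 6.1%. Three and three also reads 6/98.

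Precision of a descriptive NT-501 minus sham difference in mean IOP at one visit, in SD units, with a random participant effect and between-eye correlation ρ assumed to be 0.3 to 0.7:

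- Cohort 2, single eyes 17 and 17: half-width = 1.96 × √[2 / (32/(1 − ρ) + 17)]. For ρ = 0.7 this is 1.96 × √(2/123.7) = 0.25. For ρ = 0.3 it is 1.96 × √(2/62.7) = 0.35. With all 34 single eyes in one arm the results are 0.26 and 0.37.
- Cohort 1, study minus fellow eye, 7 pairs: half-width = 2.447 × √[2(1 − ρ)/7] = 0.72 for ρ = 0.7 and 1.09 for ρ = 0.3.

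Under these assumptions a by-arm IOP summary would be informative in Cohort 2 and only a listing aid in Cohort 1.

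**The case against.** **The plan does not say that the arms are pooled.** This is right. A reader might infer a decision to combine NT-501 and sham eyes, but Section 8.5 is silent on arm and nothing in it forbids a by-arm column. What stands is narrower: the only eye-level split written down does not separate the arms.

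**IOP is not a free-standing measured outcome.** Also right. In Section 6.1.3 it is one example of an adverse event, beside others that likewise have no cut-off, so event tables match the outcome as defined. IOP differs in being a number recorded in both eyes on a fixed schedule, so summarising it needs no new judgment.

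**Pressure events will not disappear.** A reader might infer that they would. The documents do not support that. Section 6.1.3 says: "All adverse events (AEs) will be captured from the date of the Extension Study Consent". The mild grade in Section 7.3 includes events with "no or minimal medical therapy or intervention required", and exacerbations count. Section 6.8 sends events "up to the first Extension Study visit will be added as Medical/Ophthalmic History as applicable", but those arising during the parent studies were already collected there. The period after the last parent-study visit and before extension consent is the part recorded only as history. Handling at Visit 1 is less clear, because adverse event assessment is scheduled only from Visit 2.

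**Cut-offs may exist elsewhere.** The Safety Plan (Section 7.1) and DSMC Charter (Section 7.11) are not shown and may hold IOP limits. It cannot be said that none exist. Section 7.1 describes reporting, severity grading and monitoring rather than analysis tables.

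**It can be added at reporting.** For the arm split, largely true: no data are lost and no error rate depends on it. Cut-offs are different, since they should be fixed before the values are seen.

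**Conclusion.** The point holds as a gap in the planned safety tables. Followed as written, Sections 8.4 and 8.5 give one row for 98 Cohort 2 study eyes and cannot show whether ocular events fall in NT-501 or sham eyes, except through unmasked attribution. They also leave up to 584 scheduled IOP readings without a summary. The eye counts follow from the documents; the reading total assumes full enrolment and attendance.

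The 33% to 67% range, the six-eye example and the half-widths are illustrations. They rest on an assumed allocation of one eye per arm in the 32 pairs and on an assumed correlation.

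A reader might go further and infer that the implant affects pressure or that a signal is being hidden. Nothing in the documents suggests either. The change is worth making because it improves the answer to a stated objective at little cost; the design and the efficacy analysis are not in doubt.

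**What to change.** **Section 8.5.** For Cohort 2, tabulate ocular adverse events, serious adverse events and the Section 6.1.3 outcomes separately for NT-501 eyes, sham eyes and non-study fellow eyes. Section 5 allows active treatment of sham participants if NTMT-02 is positive, so show any of their eyes that later receive NT-501 separately from the date of implantation.

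**Section 8.4.** Add a descriptive summary at each visit of measured IOP, and of change from the parent-study baseline where one exists. Use the same groups in Cohort 2, and study versus fellow eye in Cohort 1. Add counts of eyes beyond high, low and change cut-offs, taken from the readings whether or not an event was reported. The sponsor fixes the cut-offs before the data are seen, or uses those in the Safety Plan if it has them.

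No formal test is needed. A difference with a confidence interval that allows for paired eyes is optional.

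**Cost.** A few extra tables from data already collected, with no new visit or procedure. Some out-of-range readings of no clinical importance will be listed. Section 6.7 does not list the tonometry examiner as masked, so a fixed cut-off removes discretion in reporting but not any bias in the reading itself.
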